5. Add syphilis, B ultrasound testing as the optional tests when the investigator consider it necessary. Syphilis testing is recommended to be done in screening for clinical trials and the subjects with chronic kidney disease on hemodialysis will perform syphilis testing twice a year so it's optional. B ultrasound is recommended to be optional in the screening to exclude ovarian cancer.
6. Remove 'Bicarbonate' from Chemistry. Some sites do not conduct this testing and it is not critical testing for this study.
7. Add 'urine pregnancy testing' as an additional alternative besides serum pregnancy testing. Some sites prefer to use urine pregnancy testing instead of serum pregnancy testing. This will be more flexible for the investigators.
8. Modify the language of the timing of randomization to 'prior to dosing' in order to accurately clarify when the randomization happens.
9. Delete the 'Monday' to 'Sunday' in the schedule of assessments to make it more flexible for the investigators.
10. Modify the collection date of baseline iPTH up to Day -4 if needed in order to get result prior to dosing.

Amendment 1

Protocol Title: A Phase 1, Multiple Dose, Randomized, Double-blind, Placebo-controlled Study to Evaluate Pharmacokinetics, Safety and Tolerability of AMG 416 Administered Intravenously to Chinese Subjects With Chronic Kidney Disease on Hemodialysis

Amgen Protocol Number AMG 416, 20140197

Amendment Date: 08 March 2017

Rationale:

The protocol is being amended to:

1. Add IVR/IWR for this study
2. Align with the latest version of DES
3. Simplify some study procedures, for example, weight, vital sign and ECG
4. Make administrative, typographical and formatting changes throughout the protocol. Updates have been implemented to align with the current template.
5. Delete all the relevant verbiage related to M11 throughout the protocol because the team considers M11 assay as too variable
6. Delete the verbiage “ Day -2 assessments will be performed 2 days before IP administration and Day-2 and Day -1 are not HD days.” in order to provide the flexibility on the scheduling of HD prior to Day 1.
7. Some deleted text has been involved in other section (for example, a paragraph in Section 7.2 has been already involved in Section 7.5)

# **List of Abbreviations**

Abbreviation	Definition/Explanation	
AUC	area under the concentration-time curve	
AUC last	area under the concentration-time curve from time 0 to the time of the last quantifiable sample	
ВМІ	Body Mass Index	
Са	Calcium	
сСа	Total serum albumin corrected calcium concentration	
cCa x P	Corrected calcium-phosphorus product	
CI	Confidence Interval	
C max	Maximum observed concentration	
CRF	Case report form (electronic or paper)	
CTCAE	Common Terminology Criteria for Adverse Events	
CV	Coefficient of variation	
ECG	Electrocardiogram	
EOS	End of Study	
GM	Geometric mean	
IP	investigational product	
iPTH	Intact parathyroid hormone	
IV	Intravenous	
IVR/IWR	Interactive Voice/Web Response System	
MedDRA	Medical dictionary for regulatory activities	
Р	Phosphorous	
PK	Pharmacokinetic(s)	
PTH	Parathyroid hormone	
SAE	severe adverse event	
SHPT	Secondary hyperparathyroidism	
TEAE	Treatment Emergent Adverse Events	
T 1/2	Terminal elimination phase half life	
TIW	Thrice weekly	

### 1. Introduction

The purpose of this Statistical Analysis Plan (SAP) is to provide details of the statistical analyses that have been outlined within the protocol for study 20140197, Etelcalcetide (AMG 416) dated **25 May 2018**. The scope of this plan includes the primary analysis that is planned and will be executed by the Amgen Global Biostatistical Science department unless otherwise specified.

# 2. Objectives, Endpoints and Hypotheses

# 2.1 Objectives and Endpoints

Objectives	Endpoints			
Primary				
To characterize the pharmacokinetics of AMG 416 (etelcalcetide) following thrice weekly intravenous (IV) administration of 5 mg in Chinese subjects with chronic kidney disease receiving hemodialysis	Pharmacokinetic (PK) parameters of etelcalcetide in plasma including maximum plasma concentration (C max ) and area under the plasma concentration-time curve (AUC last ) over the interdialytic interval following the first and last dose			
Secondary				
To characterize the safety and	Incidence of adverse events			
tolerability of etelcalcetide following thrice weekly intravenous (IV) administration of 5 mg in Chinese	Vital signs, laboratory safety tests including cCa, and ECGs			
subjects with chronic kidney disease receiving hemodialysis	Incidence of anti-etelcalcetide antibodies			
Exploratory				

# 2.2 Hypotheses and/or Estimations

This study will adequately characterize the pharmacokinetics profile of etelcalcetide in Chinese subjects with chronic kidney disease receiving hemodialysis.

Etelcalcetide will be safe and well tolerated after multiple dose administration in Chinese subjects with chronic kidney disease on hemodialysis.

Page 6 of 20

**Product:** Etelcalcetide (AMG 416) Protocol Number: 20140197 Date: 26 November 2018

#### 3. Study Overview

#### 3.1 Study Design

This is a multiple dose, double-blind, randomized, placebo-controlled clinical study. Chinese subjects residing in Mainland China with chronic kidney disease receiving hemodialysis will be randomized in a 3:1 ratio to receive 5 mg IV of etelcalcetide or placebo thrice weekly (TIW) for approximately 4 weeks, with a subsequent follow up period of approximately 4 weeks.

#### 3.2 Sample Size

Approximately 32 subjects will be randomized in a 3:1 ratio to receive 5 mg IV of etelcalcetide or placebo three times a week (TIW) at the end of each regularly scheduled hemodialysis session for 4 weeks (12 doses).

For PK parameter estimation, 2-sided 90% confidence intervals (CI) for geometric means (GM) of PK measurements can be expressed as (GM/ $\theta$ , GM· $\theta$ ) where  $\theta$  is a measure of precision. Based on etelcalcetide study 20120330 (Cohort 3, 5 mg dose), between-subject CV for etelcalcetide AUClast (hr·  $\mu$ g/L) and Cmax ( $\mu$ g/L) (on original scale) are approximately 50.5% and 52.7%, respectively, following the Day 27 dose. Assuming the same variability for 24 subjects receiving etelcalcetide in this study, it is estimated that the precision ( $\theta$ ) of 2-sided 90% CI of geometric mean will be 1.18 and 1.19 for  $AUC_{last}$  and  $C_{max}$ , respectively.

For safety considerations, with 24 subjects receiving etelcalcetide, there will be a 21% chance of detecting an adverse event with a true incidence rate of 1% and 98% chance of detecting a more common adverse event with a true incidence rate of 15%.

#### 3.3 **Adaptive Design**

Not applicable.

#### 4. **Covariates and Subgroups**

#### 4.1 **Planned Covariates**

No covariate adjusted analyses are planned.

#### 4.2 Subgroups

No subgroup analyses are planned.

5. Definitions

5.1 Study Time Points

Informed Consent Date

The informed consent date for each subject is the date the subject signs the original informed consent for this study.

Screening Phase

The period after a subject has provided written informed consent and prior to randomization. This period may last up to 22 days and it is during this period when eligibility is determined, based on all screening tests and procedures.

**Enrollment Date** 

The date a subject is randomized to a treatment group by the interactive voice/web response system (IXRS) after they have satisfied all enrollment criteria.

Randomization Date

The randomization date is the same as the enrollment date.

Study Week

The 7-day periods beginning with Study Day 1.

Study Day 1

The first day that investigational product is administered to the subject. For subjects who did not receive any investigational product during the study, Study Day 1 will be the randomization day.

Study Day

For each subject and for a given study visit date, study day is defined as the number of days since Study Day1:

Study day = (study visit date - Study Day 1 date) + 1

If the date of interest is prior to study day 1, study day will be calculated as

Study day = (study visit date – Study Day 1 date).

**Product:** Etelcalcetide (AMG 416) Protocol Number: 20140197 Page 8 of 20

Date: 26 November 2018

Date of Last Dose IP Received

For each subject, the last investigational product dose date is defined as the date when

the last non-missing dose of investigational product is administered (zero dose is still

counted).

Primary Completion

The time when the last subject is assessed or receives an intervention for the purposes

of final collection of data for the primary analysis.

Subject-level End of Study Date

End of study for each subject is defined as the date of the subject last study assessment

in the study. The date subject ended the study is recorded on the End of Study

electronic case report form (CRF).

Study-level End of Study Date

End of study for the study is defined as the date when the last subject is assessed or

receives an intervention for evaluation in the study following any additional parts in the

study (ie, safety follow-up) as applicable.

5.2 **PK/PD Parameters** 

**AUC**last

AUClast is specifically defined in this study as the area under the concentration time

curve measured from the time of drug administration to the beginning of the next

dialysis session, following the first and last dose.

 $C_{max}$ 

 $\underline{C_{\text{max}}}$  is defined as the maximum observed **plasma** drug concentration **measured** 

between the time of drug administration to the beginning of the next dialysis

session.

5.3 **Demographics and Baseline Related Definitions** 

Age

Age will be collected as the subject's age in years at enrollment as recorded on the

eCRF.

**Product:** Etelcalcetide (AMG 416) Protocol Number: 20140197 Page 9 of 20

Date: 26 November 2018

Body Mass Index (BMI)

BMI equals a person's weight in kilograms divided by baseline height in meters squared

 $(kg/m^2)$ .

Baseline

Unless otherwise specified, for parameters/assessments scheduled to be performed on

the same day as the first administration of the investigational product, the baseline value

is the last value measured before the first administration of the investigational product on

that day.

For parameters/assessments not scheduled to be performed (or scheduled but not

performed) on the same day as the first administration of the investigational product, the

baseline value is the value from the screening period measured closest to the day of first

administration of the investigational product.

In the event that multiple pre-dose assessments are done on the same day as the first

administration of the investigational product and there is no time associated with the

assessments, the value associated with the last clinically planned event (CPE) will be

used as the baseline value.

Baseline iPTH, serum albumin and cCa is the average of predialysis assessments on

day -2 and Day 1. If screening lab tests occur within 7 days prior to start of IP, then

day -2 lab tests can be waived. Then baseline iPTH, serum albumin and cCa is the

average of predialysis assessments at screening and day 1.

Change from Baseline

The arithmetic difference between a post-baseline value and baseline for a given time

point:

Change from baseline = (post-baseline value – baseline value)

Percent Change from Baseline

The percent change from baseline for a given variable at a given time point is defined

as:

100% x [(value at a given time point – baseline value) / baseline value]

# 5.4 Other Study Related Definitions

### Corrected Total Serum Calcium (cCa)

Corrected calcium (mg/dL) = Total calcium (mg/dL) + (4 – albumin [g/dL]) x 0.8

Total serum calcium will be corrected using above formulae if the serum albumin is < 4 g/dL or 40 g/L, otherwise cCa equals total serum calcium.

#### Low Calcium Based on Corrected Calcium Values

cCa values will be used to identify cases of low calcium of different severities using the following three categories: < 7.0 mg/dL, 7.0 - < 7.5 mg/dL, and 7.5 - < 8.3 mg/dL.

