7.3.10 Clinical Chemistry, Hematology

Blood samples for clinical chemistry and hematology will be collected at screening, the day -2, and the time points specified in the Schedule of Assessments.

The tests listed below in [Table 2](#), will be conducted on samples collected and analyzed by standard laboratory procedures.

Table 2. Chemistry, Hematology

Chemistry	Hematology	Other Labs
Sodium	Red blood cells	Antidrug Antibodies
Potassium	Hemoglobin	Hep B surface antigen
Chloride	Hematocrit	Hep C antibody
Total protein	Mean corpuscular volume	HIV
Albumin	Platelets	Pregnancy
Glucose (Random)	White blood cells	Intact PTH (iPTH)
Blood urea nitrogen	Differential	25-hydroxyvitamin D
Creatinine	• Total neutrophils	PK
Total bilirubin	• Eosinophils	PT
Direct bilirubin	• Basophils	aPTT
Alkaline phosphatase	• Lymphocytes	FSH ^b
Alanine aminotransferase (ALT)	• Monocytes	Luteinizing hormone ^b
Aspartate aminotransferase (AST)		Estradiol ^b
Calcium		Syphilis ^c
Adjusted Calcium		Urea/BUN ^d
Creatinine phosphokinase		
Phosphorus		
Thyroid-stimulating hormone (TSH) ^a		

^a Only required at screening for subjects who have a history of hyper- or hypothyroidism and do not have available TSH results within 6 months prior to screening

^b Females only, and only collected if deemed necessary for confirmation of postmenopausal status as described in exclusion criteria [section 4.2.4](#)

^c Only collected at screening when investigator consider it is necessary

^d Urea/BUN measurement to be performed locally for Kt/V or URR assessment at screening, unless a qualifying Kt/V or URR measurement from within 4 weeks prior to screening assessments is available.

All clinical chemistry and hematology tests must be reviewed, signed, and dated by the Investigator or qualified designee, and all abnormal values must have clinical significance assessed. Additional safety laboratory assessments may be performed, if clinically indicated.

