9.3 Changes in Serum Calcium and Symptomatic Hypocalcemia

Investigators should assess subjects for the onset of signs and symptoms associated with low serum calcium (see [Section 6.3.1.1](#)) at each visit. When observed,

“hypocalcemia” should be reported as the adverse event, and the associated signs and symptoms will also be captured.

Any serum calcium (corrected) (cCa) ≥ 7.5 and < 8.3 mg/dL can be reported as low blood calcium; however, low a calcium result does not need to be reported as an adverse event if no action is taken, and the value is not deemed clinically significant by the investigator. If the cCa is < 8.3 mg/dL and there are symptoms of hypocalcemia then the event is to be reported as hypocalcemia and considered a serious adverse event. The associated signs and symptoms should also be captured.

Also, any cCa level < 7.5 mg/dL is to be reported as a serious adverse event of low blood calcium if there are no associated signs and symptoms, but it is to be reported as hypocalcemia if there are associated symptoms. The associated signs and symptoms should also be captured.

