10.5.6 Clinical Laboratory Tests

Subject level data for all lab tests will be provided and reviewed for each subject. Values outside the normal laboratory reference range will be flagged as high or low on the listings. Additionally serum albumin, iPTH, cCa and phosphorus measurements will be summarized by treatment group for all scheduled visits. Change and percent change from baseline may also be summarized for all post-baseline scheduled visits by treatment group, as applicable.

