#### 9. Statistical Methods of Analysis

#### 9.1 **General Considerations**

Demographics, baseline characteristics, and safety data will be summarized by treatment groups. Unless otherwise stated, the data analysis will be conducted using subjects in the Safety Analysis Set. Descriptive statistics on continuous measurements will include mean, median, standard deviation, and range, while categorical data will be summarized using frequency counts and percentages. Graphical summaries of the data may also be presented. When data are summarized by time, the values recorded against the scheduled time points listed in the protocol will be used. Descriptive

summaries will be provided to characterize all primary and secondary endpoints in this study.

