### 9.6.2 Clinical Laboratory Test Results

Serum albumin, iPTH, cCa and phosphorus measurements will be summarized by treatment group for all scheduled visits. Change and percent change from baseline may also be summarized for all post-baseline scheduled visits by treatment group, as applicable.

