# Appendix A. Reference Values/Toxicity Grades

Refer to the NCI Common Terminology Criteria for AEs (CTCAE) Version 4.0, published: May 28, 2009 (v4.03: June 14, 2010) for AE and lab shift grading and information. The CTCAE is available at the following link:

http://evs.nci.nih.gov/ftp1/CTCAE/About.html

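### Do the three low-calcium categories in SAP 5.4 need a separately written table in the laboratory analysis section?

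*SAP*

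**What the plan says.** SAP 5.4 sets the cut-offs and says that "cCa values will be used to identify cases of low calcium of different severities using the following three categories". They are below 7.0, 7.0 to below 7.5, and 7.5 to below 8.3 mg/dL.

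SAP 9.6.2 does not mention the categories: "Serum albumin, iPTH, cCa and phosphorus measurements will be summarized by treatment group for all scheduled visits", with change from baseline optional.

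SAP 9.1 gives the general rules. Safety data are presented by treatment group in the Safety Analysis Set, categorical data as counts and percentages, and every secondary endpoint gets a descriptive summary. cCa is named in a secondary endpoint (Protocol 10.1.1.2). SAP 9.1 also says: "When data are summarized by time, the values recorded against the scheduled time points listed in the protocol will be used".

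Protocol 7.3.10 allows extra tests: "Additional safety laboratory assessments may be performed, if clinically indicated". Protocol 10.5.6 provides subject-level data for all laboratory tests and adds: "Values outside the normal laboratory reference range will be flagged as high or low on the listings". SAP Appendix A points to CTCAE "for AE and lab shift grading and information".

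Protocol 9.3 governs reporting. A cCa of 7.5 to below 8.3 mg/dL "does not need to be reported as an adverse event if no action is taken" and the investigator does not consider it clinically significant. Below that band, "any cCa level < 7.5 mg/dL is to be reported as a serious adverse event of low blood calcium" if there are no symptoms. With symptoms, any value below 8.3 is reported as hypocalcemia and counted as serious.

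**The concern.** A plan that defines severity bands and then seems not to use them invites the question of where the result will appear. Hypocalcemia heads the important identified risks in Protocol 2.3.

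The planned visit summaries give mean, median, SD and range. They show the lowest value at each visit but not how many subjects were ever low. A low value found at an unscheduled test falls outside them. The adverse event tables can miss a mild, symptom-free fall that nobody acted on. The listing flags use the laboratory's reference range, not 7.0, 7.5 and 8.3. CTCAE shift grading is mentioned, but no visible section plans a shift table. If all this left low calcium uncounted, the report would understate the effect the trial most needs to describe in this population.

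**Working it through.** **1. The plan's own figures for what 24 subjects can show.** Protocol 10.2 gives a 21% and a 98% chance of seeing at least one event at true rates of 1% and 15%. With 1 − (1 − p)^24: 1 − 0.99^24 = 21.4% and 1 − 0.85^24 = 98.0%. Both reproduce, and nothing here disputes them.

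**2. Which output captures which low value.** Inputs: Protocol 9.3 and 10.5.6, SAP 5.4, 9.1 and 9.6.1. SAP 5.4 counts each subject once per event, so the adverse event tables are already counts of subjects who ever had the event.

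| Post-baseline cCa (mg/dL) | Reported as | Planned output besides visit summary and listing |
|---|---|---|
| Below 7.0 | Serious adverse event | Serious event table, by arm |
| 7.0 to below 7.5 | Serious adverse event | Serious event table, by arm |
| 7.5 to below 8.3, symptoms | Hypocalcemia, serious | Serious event table; hypocalcemia table if case numbers warrant |
| 7.5 to below 8.3, no symptoms, acted on or judged significant | Adverse event | Adverse event table by preferred term |
| 7.5 to below 8.3, no symptoms, no action, not significant | Need not be an event | Only the SAP 5.4 classification |

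SAP 9.6.1 also plans an event-of-interest table. Its term list is a separate document, so the argument does not rely on it. Two things lack another named table: the last row, and the split at 7.0.

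**3. Does the plan commit to a count for those two?** SAP 5.4 says the values will be used to identify cases in three bands. A band is a categorical safety variable on a named secondary endpoint. SAP 9.1 fixes the arms, the analysis set and the statistic for such a variable. Together they yield a by-arm count and percentage. The scheduled-time-point rule in SAP 9.1 covers data summarized by time. A classification of subjects is not such a summary, so the rule does not bar unscheduled values.

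**4. Can the residual be recovered?** Protocol 7.2.3 schedules cCa on Days 8, 15, 22, 27, 29, 34, 41 and 55, which is 8 post-baseline values per subject. That is 24 × 8 = 192 values on AMG 416 and 8 × 8 = 64 on placebo, 256 in all plus any unscheduled tests. All are listed by subject.

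**5. What could such a table support?** With no cases, the upper limit of the exact two-sided 95% interval is 1 − 0.025^(1/n): 14.2% for 0/24 and 36.9% for 0/8. With cases, taken here as an assumption, 6/24 gives 9.8% to 46.7% and 1/8 gives 0.3% to 52.7%. It describes and cannot compare.

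**6. ECG wording.** The synopsis and SAP 9.1 read as though ECGs will be summarized. Protocol 10.5.5 and SAP 9.6.5 agree on listings only and give the reason. The synopsis sends the reader to Section 10 for the methods, so the specific sections govern.

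**The case for a change.** The strongest case for a change is that visit summaries cannot answer the question of who was ever low. If k of 24 subjects are low at each of v visits, the number ever low can lie anywhere from k to the smaller of 24 and k × v. For k = 2 (an assumption) over the 8 scheduled visits, that is 2 to 16. Writing the table down would cost little and would prevent choices being made after the data are seen. In the active-controlled phase 3 study, asymptomatic decreased blood calcium was reported in 68.9% of etelcalcetide subjects and symptomatic hypocalcemia in 5.0% (Protocol 2.2.2), so most low calcium is symptom-free.

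The first point is correct about visit summaries, but they are not the only output (steps 2 and 3). The phase 3 figures are themselves adverse event rates. They show symptom-free low calcium reaching the event tables, and they do not say what share would go unreported under Protocol 9.3.

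What stands is that some detail is unstated: lowest value or value per visit, whether unscheduled values count, and who is in the denominator. These are choices for a table shell. They need care rather than a quick sentence. In the full Safety Analysis Set, putting everyone not below 8.3 into a remainder row would count dosed subjects with no post-baseline cCa as normal. The entry threshold of 8.3 is applied at screening and Day -2, not to the Day 1 value, so a later low value is not automatically new.

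**Conclusion.** No change to the plan is needed. This is a gap in detail that analysts fill sensibly from SAP 5.4 and 9.1 read together. The values without another named table are the asymptomatic, unactioned, non-significant ones of 7.5 to below 8.3 mg/dL, and the division of serious events at 7.0. Both can be derived from about 256 scheduled listed values plus any unscheduled ones. No endpoint, sample size or conclusion of this roughly 32-subject pharmacokinetic study depends on the table.

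The conclusion rests on three assumptions: that the general rule in SAP 9.1 applies to a category defined in SAP 5.4, that low values are reported as Protocol 9.3 requires, and that the serious event table is produced whatever the number of cases. SAP 9.7 shows no text in the public copy, so a table may already be planned there. The documents give no 4-week rate of low cCa at 5 mg, so the number of subjects in the residual group cannot be stated. The ECG mismatch is clerical.
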